5.5. Open-Label Extension

At Week 24 (Visit 10) or Week 28 (Visit 11), the subject may be given the option to move into the OLE treatment if the subject meets the OLE entry criteria in Section 5.5.1.

- If the subject declines the OLE, Visit 11 (Post-treatment) will be the last double-blind study visit.
- If the subject chooses to continue into the OLE, she/he must sign an OLE ICF/Accent, complete Visit 10 or Visit 11, as appropriate, and OLE Visit 1, prior to being dispensed open-label drug and receiving continued study medication application instructions. The subject will be scheduled for OLE Visit 2.
- If the subject enrolls in open-label treatment within 30 days of completion of Week 24 (Visit 10) or Week 28 (Visit 11), OLE Visit 1 will be conducted to obtain consent/assent and perform the procedures in the Schedule of Assessments. This will be considered the official date that the subject initiated OLE treatment.
- If the subject enrolls in open-label treatment > 30 days after completion of Week 28, OLE Visit 1 will be conducted in order to obtain consent/ assent, and complete the procedures detailed in the Scheduled of Events. This will be considered the official date that the subject initiated OLE treatment and the scheduling of subsequent visits will be based on this date.

5.5.1. OLE Entry Criteria

1. Subject must be able to comprehend and willing to sign the OLE Informed Consent/Accent Form (ICF).
2. Subject must continue to meet the entry criteria from the double-blind period. The SALT score and duration of disease are based on the double-blind period baseline visit.
3. Subject has not experienced any clinically significant AEs, SAEs or tolerability issues that met the study discontinuation criteria in the double-blind period.
4. Subject is capable of regrowing scalp hair in the opinion of the investigator.
5. WOCBP must have a negative UPT at entry into OLE.

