2. INTRODUCTION

Aclaris Therapeutics, Inc. is developing ATI-50002 Topical Solution for the treatment of stable patchy alopecia areata. ATI-50002 is a potent highly selective inhibitor of Janus kinase 1 (JAK1) and Janus kinase 3 (JAK3).

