5.3. Double-Blind Inclusion Criteria

Subjects must meet the following criteria to be eligible for participation in the study:

1. Able to comprehend and willing to sign an Informed Consent/Accent Form (ICF).
2. Male or non-pregnant, non-nursing female ≥ 12 years old at the time of informed consent/assent.
3. Have a clinical diagnosis of stable patchy alopecia areata (AA) defined as no current areas of spontaneous regrowth.
4. Have a Severity of Alopecia Tool (SALT) score of at least 15% up to 95% total scalp hair loss determined by the study investigator at baseline.
5. Have an assessment of “no hair” or “a little hair” in the target scalp patch based on both the Clinician and Subject Alopecia Scalp Appearance Assessment (AAA).
6. Have a duration of the current episode of scalp hair loss of a minimum of 6 months and a maximum of 12 years.
7. If a woman of childbearing potential (WOCBP), must have a negative serum pregnancy test at Screening (Visit 1) and a negative urine pregnancy test at Baseline (Visit 2) and agree to: use a highly effective method of birth control for the duration of the study; not be planning a pregnancy during the study duration and use contraception for 30 days after last application of study medication. (Refer to Section 10).

8. Be in good general health and free of any known disease state or physical condition which, in the investigator's opinion, might impair evaluation of the subject or which might expose the subject to an unacceptable risk by study participation.
9. Be willing to maintain the same hair style throughout the study period. Subjects who shave their scalp must be willing to refrain from shaving their scalp for at least one week or longer prior to each study visit, as determined by the investigator based on visible scalp hair growth. Hair trimming outside the treatment areas to maintain the current hair style is permitted.
10. Be willing and able to follow all study instructions and to attend all study visits.
11. Subjects taking hormonal replacement therapies must be on stable doses for 6 months prior to enrollment and remain on the same maintenance dose throughout the study.
12. Subjects taking thyroid replacement medication must be on stable doses for 6 months prior to enrollment and remain on the same maintenance dose throughout the study.

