10. History of a serious local infection (e.g., cellulitis, abscess) or systemic infection including but not limited to a history of treated infection (e.g., pneumonia, septicemia) within 3 months prior to Baseline (Visit 2). Subjects on an antibiotic for a nonserious, acute local infection must complete the course prior to enrollment into the study.
11. Positive for HIV, Hepatitis B or C. Subjects with serologic evidence of Hepatitis B vaccination (Hep B surface Ab without the presence of Hep B sAg) will be allowed to participate.
12. Herpes zoster or cytomegalovirus (CMV) that resolved less than 2 months before study enrollment. Subjects with a history of frequent outbreaks of Herpes Simplex Virus (defined as 4 or more outbreaks a year).
13. Clinically significant laboratory abnormalities at screening that, in the opinion of the Investigator, would make the subject a poor candidate for the study.
14. Subjects with absolute neutrophil count <1,800/mL or platelet count <130,000/mL.
15. Subject unable to comply with the following required washout periods:

Therapy/Medication	Washout Period
Systemic Therapies	
Disease Modifying Anti-Rheumatic Drugs (DMARDs), Biologics or immunosuppressants, such as: anakinra, adalimumab, azathioprine, corticosteroids, cyclosporine, etanercept, infliximab, methotrexate, TNF inhibitors, ustekinumab	1 month or 5 half-lives whichever is greater
Plaquenil	2 months
JAK inhibitors (oral or topical)	6 months
Intralesional Steroids (Scalp)	
Topical Treatments on the Scalp	
Anthralin, bimatoprost, corticosteroids, diphencyprone, diphenylcycloprophenone (DPCP), Squaric acid dibutylester (SADBE), minoxidil, pimecrolimus, tacrolimus	1 month
Phototherapy, Laser Therapy, Excimer Laser	3 months

16. Participation in an investigational drug or device trial in which administration of an investigational study drug or device occurred within 30 days or 5 half-lives (whichever is longer) of Screening (Visit 1). Subjects who have participated in a study of an investigational drug, device or biologic agent for alopecia areata within 1 year of screening will be eligible to participate only with individual permission from the Medical Monitor.
17. Sensitivity to any of the ingredients in the study medications.
18. History of or current alcohol or drug abuse within 2 years of assessment for study enrollment.

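### OLE entry criterion 2 does not tie the target-patch rating to the double-blind baseline, so as written it bars target-patch responders from the extension

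*Protocol*

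**What the plan says.** Protocol 5.5.1, criterion 2, and the matching Synopsis item state: "Subject must continue to meet the entry criteria from the double-blind period". The next sentence gives the only exceptions: "The SALT score and duration of disease are based on the double-blind period baseline visit". Section 5.5 makes the offer of open-label treatment conditional on these criteria. The OLE schedule in 6.3 lists an inclusion/exclusion check on all three routes through OLE Visit 1.

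One of the criteria carried forward is inclusion 5 in Protocol 5.3: "Have an assessment of “no hair” or “a little hair” in the target scalp patch", judged on both the clinician and the subject AAA. It names no visit. By contrast, inclusion 4, the SALT criterion, already carries its own timing: "total scalp hair loss determined by the study investigator at baseline".

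Protocol 8.1.4 schedules both AAA ratings at baseline, Weeks 4, 12 and 24 (Visit 10), and then OLE Visits 4 to 6. SAP 5.2.5 defines a target-patch responder as a subject who improves by at least 2 points on the Scalp-ClinRO or the Scalp-PRO, which are the SAP's names for the two AAA versions. SAP 5.2.9 summarises the OLE descriptively, including the target-patch categories, with change measured from study Day 1 and from Visit 10.

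**The concern.** A requirement for little or no hair in the target patch makes sense for enrolling subjects into the double-blind period. Carried to the end of 24 weeks of treatment, it selects against the outcome the drug is meant to produce. The Version 8.0 entry in the amendment history says the OLE is there to give vehicle subjects a chance at active drug and to let active-arm subjects continue for longer. An entry rule that turns away those whose target patch has regrown works against the second aim. It also sits oddly beside OLE criterion 4, which asks the investigator to judge that the subject can regrow scalp hair.

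Two things are at stake: which subjects may enter, and who is represented in the OLE summaries. If sites read the rule differently, the OLE cohort will differ by site. Strict sites would contribute no one whose target patch had reached *some hair* by either rating, so the target-patch results and the change from Visit 10 would describe a population with those responders removed.

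**Working it through.** The plan gives no figure on this point. The check is a reading of the criteria plus a count over the AAA categories.

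**1. Is inclusion 5 carried forward?** Criterion 2 refers to the double-blind entry criteria without limitation and excepts SALT score and disease duration. Inclusion 5 is not excepted.

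**2. Does inclusion 5 limit itself to baseline?** Not in 5.3 or in the Synopsis. The SALT criterion does name baseline and was still given an express exception. A site could reasonably conclude that a criterion with no stated visit and no exception is to be judged on current status.

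**3. Is there a current rating to apply?** Yes at Visit 10 (Day 169), where both AAA versions are scheduled. None is scheduled at Visit 11 (Day 197) or OLE Visit 1. For entry at Visit 11 the latest scheduled rating is therefore nominally 197 − 169 = 28 days old.

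**4. Which ratings fail?** The five ordered categories are *no hair*, *a little hair*, *some hair*, *most hair* and *full hair*. The first two qualify, and both raters must give one of them.

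- Possible improvements from *no hair*: 4. From *a little hair*: 3. Total: 4 + 3 = 7.
- Only *no hair* to *a little hair* stays within the qualifying pair, so 7 − 1 = 6 of the 7 fail.
- Improvements of at least 2 categories from *no hair*: 3 (to *some*, *most* or *full*). From *a little hair*: 2 (to *most* or *full*). Total: 3 + 2 = 5, and all 5 fail.

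An improvement of 2 categories from the lowest level already reaches *some hair*. A 2-point responder on either rating therefore cannot satisfy inclusion 5 at the same visit. These counts are of scale transitions and say nothing about how many subjects make them.

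**5. What does other text say about timing?** Section 8.1.3 places the subject's qualifying target-patch rating at Baseline (Visit 2). Section 8.1.4 says the same for both raters. Section 3.1 explains the target patch as a device for enrolling subjects with less extensive loss on a common baseline rating. All three point to a baseline-only requirement, but criterion 2 neither refers to them nor is changed by them.

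**The case against.** The strongest reply is that nobody would apply the rule this way. Sections 8.1.3 and 8.1.4 fix the rating at baseline. No AAA is scheduled at Visit 11 or OLE Visit 1, although SALT and ALODEX are repeated on the route with a gap of more than 30 days. The Synopsis describes completers of Visit 10 or 11 as eligible. On this view the SALT exception only repeats what inclusion 4 already says, and proves little about items left off the list. This stands as evidence of intent and is why the point is minor. It does not remove the conflict: 5.5.1 is the operative entry rule, a Visit 10 rating is available, and 13.4 tells investigators not to depart from the protocol without approval.

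Two wider readings are tempting, and the documents support neither.

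- **Washout.** Exclusion 15 ("Subject unable to comply with the following required washout periods") lists "JAK inhibitors (oral or topical") at 6 months, and the Introduction says "ATI-50002 is a potent highly selective inhibitor of Janus kinase 1 (JAK1) and Janus kinase 3 (JAK3"). A reader might infer that active-arm subjects entering at Visit 10 or 11 are all barred. But 5.6.2, whose Table 1 has the same row, says the listed therapies are also not allowed during the study. If the row included study medication, the double-blind treatment itself would be prohibited. The row must mean other JAK inhibitors. SAP 5.2.9 fits this, since it plans active-arm groups entering within 7 days of finishing double-blind treatment.
- **Regrowth.** Inclusion 3 describes stable disease as "defined as no current areas of spontaneous regrowth". A reader might infer that any regrowth on study disqualifies. By its own wording the criterion covers spontaneous regrowth only. That a blinded investigator might misattribute drug-induced regrowth is speculation, and waiving the criterion would be a real change of eligibility.

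**Conclusion.** The concern holds for the target-patch criterion alone. As written, OLE criterion 2 excludes any subject whose target patch is rated *some hair* or better by either rater at Visit 10, including every 2-point target-patch responder by either rating. This conflicts with 8.1.3, 8.1.4 and the stated purpose of the OLE.

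The conclusion assumes that a site applies criterion 2 as worded and uses the Visit 10 AAA. The documents do not show that any site would do so, and they give no basis for estimating how many subjects would be refused. The consequence is limited to OLE access and the make-up of the descriptive OLE summaries. The double-blind primary and secondary analyses, sample size and error rate are not affected. Severity is minor.

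**What to change.** In the second sentence of criterion 2, in both 5.5.1 and the Synopsis, add *target-patch AAA rating* to the items fixed at the double-blind baseline, so that the list reads SALT score, target-patch AAA rating and duration of disease. A note that the washout list does not refer to study medication would be optional clarification only. Inclusion 3 should stay as it is.

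The change is one short phrase in two places, with no added visits, procedures or analyses. An amendment needs IRB/EC approval under 13.1, across approximately 27 sites. An administrative letter, a route this study has already used, may be enough if the sponsor and the IRB accept the change as a clarification.

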5.6. Previous and Concomitant Medications and Therapies

At Screening (Visit 1), the Investigator or designee will question the subject to ensure they have not used any excluded therapies (Section 5.6.2).

5.6.1. Permitted Concomitant Medications and Over the Counter Products (OTC)

Concomitant therapies are any new or existing therapies received from Screening (Visit 1) until Week 28 (Visit 11). Concomitant therapies include drug (e.g. prescription and over the counter [OTC]), and non-drug (e.g., chiropractic, physical therapy, energy-based treatments).

Subjects will be allowed to take medications not restricted by the protocol as long as they have been on a stable dose prior to study entry. Vitamins, minerals, and dietary supplements are permitted while on study if the subject has been on a stable dose prior to study entry and, in the opinion of the Investigator, will not affect the safety or efficacy of the subject during the study. Topical hair and scalp products (shampoos, conditioners, styling products) should be reviewed by the Investigator and are permitted if, in the Investigator's opinion, they will not affect the safety or efficacy of the subject during the study. Use of hair dyes is permitted during the study if the subject uses the same hair dye throughout the study. If in the opinion of the Investigator, the hair dye interferes with study assessments the subject may be directed to wait until after the study visit to dye his or her hair. Efforts should be made to keep the hair care regimen the same throughout the duration of the study.

Topical therapies such as topical corticosteroids are permitted if they are not applied on or near the scalp. Inhaled or intranasal corticosteroids are allowed in the study.

Prior permitted concomitant medications taken within 30 days of beginning treatment with ATI-50002 Topical Solution will be documented in the subject's source document and eCRF. In addition, any new permitted medications administered during protocol treatment and through end of study (Week 28 (Visit 11) or OLE Visit 6) will be documented in the subject's source document and eCRF.

5.6.2. Prohibited and/ or Restricted Medications

Any medication, shampoo or hair product known to affect hair growth in AA is prohibited throughout the study period. Subjects who are on a chronic stable dose of finasteride for benign prostatic hypertrophy for greater than 1 year are eligible for enrollment in the study as long as they maintain the same stable dose throughout the study. Since subjects with known AGA are excluded from the study, treatment with finasteride for alopecia during the study or within one year prior to study enrollment is prohibited. A list of medications and therapies that require a specific washout period prior to study entry and are not permitted during the study is in **Table 1**.

Table 1: Prohibited Medications

Therapy/Medication	Washout Period
Systemic Therapies	
Disease Modifying Anti-Rheumatic Drugs (DMARDs), Biologics or immunosuppressants, such as: anakinra, adalimumab, azathioprine, corticosteroids, cyclosporine, etanercept, infliximab, methotrexate, TNF inhibitors, ustekinumab	1 month or 5 half-lives whichever is greater
Plaquenil	2 months

JAK inhibitors (oral or topical)	6 months
Intralesional Steroids on the Scalp	1 month
Topical Treatments on the Scalp	
Anthralin, bimatoprost, corticosteroids, diphenycprone, diphenylcycloprophenone (DPCP), Squaric acid dibutylester (SADBE), minoxidil, pimecrolimus, tacrolimus	1 month
Phototherapy, Laser Therapy, Excimer Laser	3 months

5.7. Subject Identifier (SI)

The Investigator will assign a unique five-digit subject identifier (SI) to each subject at Screening (Visit 1).

The SI format will be NN-NNN, using leading zeroes as appropriate, where:

- The first 2 digits are the investigational center site number assigned by Aclaris
- The final 3 digits are the subject number (SN), assigned in ascending numerical order by the Investigator or designee, without omitting or repeating any number, starting with 001.

For example, the SI for the twenty-third subject that signs an informed consent/ assent form at site number 01 would be 01-023. The subject will be identified using the SI in all study documentation for the duration of the study.

5.8. Replacement Subjects

Subject enrollment will continue until approximately 120 subjects have been randomized. Subjects who are randomized and do not complete the study will not be replaced.

5.9. Subject Withdrawal Criteria

Subjects will be informed that they are free to withdraw from the study at any time and for any reason. The investigator may remove a subject from the study if, in the investigator's opinion, it is not in the best interest of the subject to continue the study. Examples of other reasons subjects may be discontinued from the study are: a change in compliance with an inclusion or exclusion criterion, occurrence of AEs, occurrence of pregnancy, use of a prohibited therapy or subject is unwilling or refuses to continue with the protocol defined study visits and/or subject withdraws consent/ assent (Refer to Section 9.2.4 for study medication discontinuation or termination criteria).

In case of premature discontinuation from double-blind study participation, all efforts will be made to perform all Visit 10 (Week 24) assessments. For premature discontinuations occurring in the OLE, all efforts will be made to perform all OLE Visit 6 assessments. The date the subject is withdrawn from the study and the reason for discontinuation must be recorded in the subject's electronic case report forms (eCRFs). All withdrawn subjects with ongoing AEs will be followed until the event has resolved or stabilized, until the subject is referred to the care of a local health care professional, or until a determination of a cause unrelated to the study medication or study procedures is made.

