9.1.4. Adverse event reporting period

The investigator must start reporting non-serious AEs with the subject's first study medication application and continue reporting until the end of the subject's last study visit. Reporting for SAEs must start when the subject signs the ICF and continue until the end of the subject's last visit.

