10.2. Highly Effective Methods of Birth Control

The Investigator or subinvestigator will discuss the potential risk factors associated with pregnancy and the importance of maintaining a highly effective method of contraception throughout the study with all WOCBP (for example, those which result in a low failure rate - i.e., less than 1% per year when used consistently and correctly). All WOCBP must use a highly effective method of birth control during the study and for 30 days after the final application of study medication in a manner such that risk of failure is minimized.

Highly effective methods include:

- Combined (estrogen and progestogen containing) hormonal contraception associated with inhibition of ovulation:
 - oral
 - intravaginal
 - transdermal
- Progestogen-only hormonal contraception associated with inhibition of ovulation:
 - oral
 - injectable
 - implantable
- intrauterine device (IUD)
- intrauterine hormone-releasing system (IUS)
- vasectomized partner¹
- sexual abstinence²

¹Vasectomized partner is a highly effective birth control method provided that partner is the sole sexual partner of the WOCBP trial participant and that the vasectomized partner has received medical assessment of the surgical success.

² Sexual abstinence is considered a highly effective method only if defined as refraining from heterosexual intercourse during the entire period of risk associated with the study treatments. The reliability of sexual abstinence needs to be evaluated in relation to the duration of the clinical trial and the preferred and usual lifestyle of the subject.

WOCBP must be on a highly effective method of birth control for the following timeframes prior to study entry:

- Implants (on a stable dose for ≥ 30 days)
- Injectables (on a stable dose for ≥ 30 days)
- Patches (on a stable dose for ≥ 30 days)
- Combined oral contraceptives (on a stable dose for ≥ 30 days)
- Intrauterine devices (inserted for ≥ 30 days).

Prior to trial enrollment, WOCBP must be advised of the importance of avoiding pregnancy during trial participation and of the potential risk factors associated with pregnancy while in the study. The subject must sign an informed consent/ assent form documenting this discussion. During the trial, all WOCBP will be instructed to contact the investigator immediately if they suspect they might be pregnant (*e.g.*, missed or late menstrual period).

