#### Adverse Event (AE)

An AE is any untoward medical occurrence in a subject administered a study medication(s) and which does not necessarily have a causal relationship with the study medication. An AE can therefore be any unfavorable and unintended sign or symptom associated with the use of a study medication (including an abnormal laboratory finding), whether related to the study medication. Thus, any new, clinically significant worsening of an existing sign, symptom or disease, should be considered an AE. Every new episode or clinically significant worsening of a chronic condition (*e.g.*, headaches, seasonal allergies, depression, or hypertension) should be reported as a separate AE, even if the condition is reported in the subject's medical history.

Treatment-Emergent Adverse Event (TEAE)

For the interim analysis of the DB treatment period, any recorded AE that occurs on or after the initiation of study medication and within 31 days after the date of Visit 10 or after the date of last DB dose of study medication will be considered treatment-emergent. For the OLE period analysis, an AE that occurs on or after the initiation of OLE study medication and within 31 days after the date of last dose of study medication will be considered treatment-emergent.

Treatment-emergent Laboratory Abnormalities

A treatment-emergent laboratory abnormality is defined as a result in which the baseline value is within normal laboratory limits and the post-baseline value is outside normal laboratory limits. If the relevant baseline assessment is missing, then any post-baseline value outside normal laboratory limits is treatment-emergent.

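### After early withdrawal from the double-blind period, no visit or contact is clearly specified to collect new-onset AEs and SAEs, although the SAP counts events for 31 days after the last dose

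*Protocol*

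**What the plan says.** - **Exit visit.** Protocol Section 5.9: "In case of premature discontinuation from double-blind study participation, all efforts will be made to perform all Visit 10 (Week 24) assessments". No timing after the last application is given, and Visit 11 is not mentioned. For the open-label extension (OLE) the rule differs: "For premature discontinuations occurring in the OLE, all efforts will be made to perform all OLE Visit 6 assessments". OLE Visit 6 is the post-treatment visit of that period.
- **End of reporting.** Protocol Section 9.1.4 stops non-serious AE reporting at the end of the last study visit. For SAEs: "Reporting for SAEs must start when the subject signs the ICF and continue until the end of" the last visit. Section 9.2.2 limits the investigator's SAE duty to events that occur in this reporting period.
- **Post-treatment visit.** In the schedules (Protocol Section 6.3, SAP Section 1.2), Visit 10 (Day 169) is a treatment visit. Visit 11 (Day 197) is the post-treatment visit, with AEs, laboratory tests, ECG and urine pregnancy test.
- **Analysis window.** SAP Section 3.3.6, for the double-blind period, takes AEs from first dose and "within 31 days after the date of Visit 10 or after the date of last DB dose of study medication will be considered treatment-emergent".
- **What is followed after withdrawal.** Protocol Section 5.9: "All withdrawn subjects with ongoing AEs will be followed until the event has resolved or stabilized", with referral to local care or a finding of an unrelated cause as alternative end points.

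**The concern.** The SAP's window runs past the point where the Protocol stops collecting for these subjects. Take a subject who is withdrawn, attends the exit visit, and has a new infection ten days later. The event falls inside the SAP's 31 days if the exit visit came within three weeks of the last dose. It falls outside the reporting period of Section 9.1.4, so the site has no duty to record it and no scheduled contact at which to hear of it.

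Safety is part of the primary objective (Protocol Section 4.1). Follow-up for new events is least assured in a group that includes subjects withdrawn for safety reasons. SAP Section 5.3.1 reports numbers and percentages of subjects with an event and plans no adjustment for time under observation. If early withdrawal differed between arms, the tables would not correct for it.

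**Working it through.** **1. Who is affected.** Protocol Section 9.2.3 takes subjects with listed ECG findings off study medication and out of the study. It asks for discontinuation and follow-up procedures, but no section defines them. Section 5.9 allows discontinuation from the study for AEs, among other reasons. Sections 7.9.1 (broken blind) and 8.4.4 (positive pregnancy test) also end participation. For all of these during the double-blind period, the exit visit is the only visit Section 5.9 names. Section 9.2.4.2 is different: it stops study medication and does not say that the subject leaves the study.

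**2. The plan's own day count.** Protocol Section 6.4 gives a maximum of 200 days from Baseline to Visit 11: 197 + 3 = 200. This reproduces.

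**3. Completers seen at Visit 11.**
- Nominal interval from Visit 10 to Visit 11: 197 - 169 = 28 days.
- With ±3-day windows, shortest: (197 - 3) - (169 + 3) = 194 - 172 = 22 days.
- Longest: (197 + 3) - (169 - 3) = 200 - 166 = 34 days.
- Days of the 31-day window left uncovered, if the last dose is at Visit 10: nominally 31 - 28 = 3 (10%), and 31 - 22 = 9 at the shortest interval.

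**4. Early double-blind withdrawals.** Let k be the number of days from the last dose to the exit visit. The documents do not give k, so a range is shown. Uncovered days = 31 - k.

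| k (assumed) | Uncovered days | Share of 31 days |
|---|---|---|
| 0 | 31 | 100% |
| 3 | 28 | 90% |
| 7 | 24 | 77% |
| 14 | 17 | 55% |
| 28 | 3 | 10% |

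The last row is what a visit at the Visit 11 interval would achieve. The table uses the SAP's last-dose limb. The SAP does not say whether an exit visit counts as Visit 10; if it does, the other limb runs 31 days from the visit at which reporting ends.

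**5. Tests.** Laboratory tests, ECG and urine pregnancy test are scheduled at Visit 11. After an early exit visit, no further scheduled set is named. Contraception, by contrast, is required for 30 days after the last application: "All WOCBP must use a highly effective method of birth control during the study and for 30 days after the final application" of study medication (Protocol Section 10.2).

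**The case against.** A reader might infer that subjects stopped for toxicity have no post-treatment collection at all. The documents do not support that.

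- The event that led to the stop is followed. Section 5.9 follows ongoing AEs, Sections 9.2.1 and 9.2.2 follow related AEs and SAEs past the last visit, and Section 9.2.4.1 requires repeat testing of confirmed laboratory abnormalities until they return to normal or baseline.
- Infection, blood-count and liver criteria (Section 9.2.4.2) stop the drug only. A subject who stays in the study keeps the scheduled visits, including Visit 11.
- The exit visit may itself fall after the last dose, and it collects AEs.
- Section 10.2 requires every pregnancy to be reported and does not tie this to the last visit. What is missing is a scheduled test or contact, not the duty to report.
- Early OLE withdrawals are already sent to the OLE's post-treatment visit; only its timing is open.

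All of this stands, and it confines the point to new-onset events and scheduled tests after early double-blind withdrawal.

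Two further arguments stand in part. First, the Protocol synopsis and SAP Section 1.1 send subjects who are not eligible for the OLE to Visit 11, and Section 5.5.1 bars those who met discontinuation criteria. Read literally, that covers early toxicity withdrawals and would extend their reporting to Visit 11. But the sentence concerns OLE entry after Visit 10 or 11, while Section 5.9 is the specific rule for leaving early. Visit 11 is also fixed at Day 197: for a subject who stops at Week 8 (Day 57) it comes 197 - 57 = 140 days later. At best the two passages conflict.

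Second, the SAP window classifies AEs that have been recorded; it does not promise 31 days of collection, and even completers are nominally 3 days short. That is correct, but the shortfall for an early withdrawal can be several times larger.

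**Conclusion.** The point holds in this limited form. For subjects withdrawn early from the double-blind period, the Protocol does not clearly provide for collecting new-onset AEs and SAEs after the exit visit, or for post-treatment laboratory tests, ECG and pregnancy test, while the SAP would count events for 31 days after the last dose. The gap is 31-k days per subject, between 31 and 17 days for k from 0 to 14. The 31-day figure is a worst case that needs the exit visit on the last dosing day.

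No total in subject-days can be given, because the documents state neither k nor a withdrawal rate. Nor do they show that active arms would have more early withdrawals, so a downward bias in their event counts is possible but not established. The matter is modest in size and worth fixing because the correction is cheap.

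**What to change.** 1. **Protocol Section 9.1.4:** set the AE and SAE reporting period to end at the later of the last study visit and 31 days after the last application, so that it matches the SAP window.
2. **Protocol Section 5.9:** for early double-blind withdrawals, add to the exit visit a post-treatment contact timed from the last application. This would be the Visit 11 assessments or, at minimum, a telephone contact for AEs, SAEs and pregnancy at the end of the 31-day window.
3. **Reconcile the related text:** align the synopsis sentence on Visit 11 (and SAP Section 1.1) with Section 5.9, define the follow-up that Section 9.2.3 asks for, and state in SAP Section 3.3.6 which limb of the window applies to a subject who leaves early.
4. **OLE:** state the timing of OLE Visit 6 relative to the last application for early withdrawals. Nothing more is needed there.

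The cost is protocol wording and one extra contact per early double-blind withdrawal, using assessments already in the schedule. Some subjects will refuse, particularly those who withdraw consent.
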